## **13.6 Adverse Event Outcome Classification**

Outcome of the event will be defined according to the following:

- **Fatal:** This event is determined to be the cause of death.
- **Not Recovering/Not Resolved:** The event has retained pathological conditions resulting from the prior disease or injury.
- **Recovered/Resolved:** The event has fully resolved at the end of the study.
- **Recovering/Resolving:** The event is ongoing at the end of the study.
- **Unknown:** The event has been unclassified at the end of the study.

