## **11.13 Subject Exit, Withdrawal or Discontinuation**

### **11.13.1 Study Exit**

A study exit CRF is required for all subjects. Prior to exiting a subject from the study, it is recommended to follow the subject until all ongoing system and/or procedure related AEs are resolved or unresolved with no further actions planned. Following exit, subjects will continue to receive standard medical care. Upon exiting from the study, no further study data will be collected or study visits will occur for the subject. All data available through the time of the subject's exit will be used for analysis.

Subjects are urged to remain in the study as long as possible but may be exited from the study for any of the following situations:

- Study completed
- Subject lost to follow-up
- Subject death
- Subject chooses to withdraw (e.g., consent withdrawal)
- Investigator deems withdrawal necessary (e.g., medically justified, inclusion/exclusion criteria not met, failure of subject to maintain adequate study compliance)
- Mesh removal

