## **12. Risks and Benefits**

### **12.1. Potential Risks**

Medtronic follows rigorous Quality Assurance and Control procedures throughout the life of a product, from the business analysis phase through development, market release, and post-market surveillance. For studies following ISO 14155, the risk analysis process for the ProGrip™ self-gripping polyester mesh is being performed in accordance with ISO 14971, and will ensure that the level of risk is acceptable prior to starting the study. The residual risks have been classified as acceptable in the worst cases.

Possible additional risks for participating in this study include the following (although others are possible): hematoma, seroma, adhesion, infection, fistula, chronic pain, inflammation, and recurrence, allergic

reaction to the components of the product and urinary retention (which may occur with the use of anesthetics). Details can be found in the device IFUs (Section 19.2).

For subjects that are operated for an oncologic colorectal procedure, the abdominal CT-Scan is part of standard of care. For other procedures, as a result of participation in this study, subjects may be exposed to radiation from x-ray procedures. In addition to the routine procedures, the x-ray exams used for this study include a CT scan evaluation of the abdominal cavity. These x-ray exams deliver up to a total radiation dose of approximately 8 mSv each, and subjects will undergo 1 CT scans at the 1 and 2 year post-operative visits. A milliSievert (mSv) is a unit of radiation dose. For comparison, the average person in France receives 2.9mSv each year from natural sources of radiation. A slight increase in cancer risk may exist for people exposed to radiation.

Following the fluoroscopic procedure, as with any X-ray exposure in everyday life, the skin area exposed to those x-rays could react to produce an effect similar to a sun burn. A skin reaction, if it occurs at all, could show up from a few hours to a few weeks after the procedure, and usually goes away on its own. If a skin reaction is found the subject should promptly report this to the study physician.

The mesh will not stretch to accommodate growth so it may be inappropriate to have a mesh implanted if the subject is planning a future pregnancy. A pregnancy after a laparotomy is a risk factor for developing an incisional hernia.

There may be additional risks related to this study that are not yet known.

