## **13.3 Processing Updates and Resolution**

For any changes in status of a previously reported adverse event or DD (i.e. change in actions taken, change in outcome, change in relatedness), information needs to be updated on, or added to a new AE or DD paper form. All AEs must be followed until the AE has been resolved, is unresolved with no further actions planned, the subject dies or exits the study, or until study closure, whichever occurs first.

In the event that a subject is exited from the study prior to study completion, all efforts should be made to continue following the subject until all unresolved system or procedure related AEs, as classified by the investigator, are resolved, unresolved with no further actions planned, or 30 days, whichever occurs first.

At the time of study exit, all collected adverse events that are unresolved must be reviewed and an update must be reported.

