**Table 5: Reporting requirements of applicable events and device deficiencies.**

Report	Responsible party	Submit to	Description / Time constraints
ADE, or DD	Investigator	Medtronic	Notify within 24h of notification of the event via data entry into Club Hernie database and AE form, telephone call and fax
	Medtronic	EC	Review within 48 hours per EC requirements
SAE, SADE, or Device Deficiency that might have led to a SADE	Investigator	Medtronic	Notify within 24h of notification of the event via data entry into Club Hernie database and AE form, telephone call and fax
	Medtronic	EC	Review within 48 hours per EC requirements Per EC requirements
U(S)ADE	Medtronic	IEC	Review within 48 hours per EC requirements Per EC requirements
	Medtronic or designee	Alternate applicable regulatory body	Report the results of an evaluation to EC and all participating investigators within 7 working days after Medtronic first receives notice of the effect, and 2 days if the U(S)ADE indicates an imminent risk of death, serious injury or serious illness and requires prompt remedial action.

Assessment of the occurrence of an AE will be based on changes in the subject's abbreviated physical examination, laboratory results and/or signs and symptoms. Adverse events will be monitored until a subject completes the study unless the Investigator determines the event is related to the device, in which case they will be monitored until resolution, if possible. Medical care will be provided, as defined in the informed consent, for any AE related to study participation. Adverse events will be collected on the Club Hernie database, and on an AE paper form to be sent to the sponsor and applicable source documentation. AE data will include but is not limited to; date of the AE, treatment, resolution, assessment of both seriousness and relationship to the investigational medical device. To the extent possible, the event to be recorded and reported is the event diagnosis as opposed to event symptoms (e.g., fever, chills, nausea and vomiting in the presence of a clinically diagnosed infection is to be reported as infection only). AEs occurring at procedure and up to and including 24 months follow-up will be recorded.

The following should not be considered an AE:

- A condition requiring a preplanned procedure unless the condition worsened since screening
- A preexisting condition found as a result of screening, unless the condition has worsened since enrollment.

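### Two adverse event outcome definitions in Protocol 13.6 do not match their labels and can both apply, so a persistent, non-improving event can be recorded as resolving

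*Protocol*

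**What the plan says.** Protocol 13.6 lists five outcomes for an adverse event: *Fatal*, *Not Recovering/Not Resolved*, *Recovered/Resolved*, *Recovering/Resolving* and *Unknown*. Apart from *Fatal*, the definitions are:

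- *Recovered/Resolved*: "The event has fully resolved at the end of the study"
- *Recovering/Resolving*: "The event is ongoing at the end of the study"
- *Not Recovering/Not Resolved*: "The event has retained pathological conditions resulting from the prior disease or injury"
- *Unknown*: "The event has been unclassified at the end of the study"

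Protocol 13.3 says when follow-up of an event ends: when it has resolved, or when it "is unresolved with no further actions planned, the subject dies or exits the study, or until study closure, whichever occurs first". For subjects who leave early, 13.3 asks for efforts to keep following related events for up to 30 days. It also requires every event still unresolved at exit to be reviewed and updated. Protocol 11.13.1 recommends following related events, before exit, to resolution or to the point where nothing more is planned.

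Protocol 12.1 names these among the possible risks: "hematoma, seroma, adhesion, infection, fistula, chronic pain, inflammation, and recurrence".

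SAP 7.9 summarises adverse events by number, severity, seriousness and relationship. SAP 7.10 adds listings and a MedDRA breakdown by System Organ Class and Preferred Term. Neither section plans a table by outcome category.

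**The concern.** A reader takes *Recovering/Resolving* to mean that the subject is getting better. The definition says only that the event has not ended. Site pain that is unchanged at the last visit, or an infection that is worse, meets it exactly.

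The category that ought to hold such events is worded around something retained from something prior. That describes sequelae better than an event still running its course. A site that goes by the definitions and a site that goes by the labels can therefore code the same subject differently.

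This matters for three reasons:

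- The secondary objective is to confirm safety, and several of the risks named in 12.1 (chronic pain, infection, fistula, inflammation) can persist.
- AE collection is restricted to device- and procedure-related events (Protocol 13.1 and 16.1), so any miscoding falls on the events that bear on the mesh.
- Protocol 14 appoints no Clinical Events Committee, so no independent adjudication is planned that would even out the coding.

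**Working it through.** No arithmetic applies. The check takes four states that an event can be in at last contact and compares the category reached from the definition with the one reached from the label.

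| State at last contact | By definition (13.6) | By label |
|---|---|---|
| Ongoing, improving | *Recovering/Resolving* | *Recovering/Resolving* |
| Ongoing, unchanged | *Recovering/Resolving* is met; *Not Recovering/Not Resolved* is arguable | *Not Recovering/Not Resolved* |
| Ongoing, worsening | *Recovering/Resolving* is met; *Not Recovering/Not Resolved* is arguable | *Not Recovering/Not Resolved* |
| Acute event over, residual effect remains | *Not Recovering/Not Resolved* | No label clearly fits |

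1. **Definition against label.** In rows 2 and 3 the two routes diverge. The only definition met without interpretation is the one whose label signals improvement.
2. **Other categories.** *Recovered/Resolved* needs full resolution and *Unknown* is for unclassified events, so neither takes rows 2 and 3.
3. **Overlap.** An ongoing event may also involve a retained pathological condition. It then meets two definitions at once, and 13.6 has no tie-break.
4. **Link to the follow-up rules.** Protocol 13.3 and 11.13.1 both recognise an event left unresolved because no further action is planned. The *Not Resolved* label suits that state, but the definition beneath it does not describe it. Because 13.3 requires unresolved events to be updated at exit, these are the events for which the list matters most.
5. **Reach into the analysis.** The AE summaries in SAP 7.9 and 7.10 use number, severity, seriousness, relationship, System Organ Class and Preferred Term. An event with the wrong outcome code is still counted once, with these attributes unchanged. The SAP does not specify the columns of the listings, so outcome may or may not appear there.
6. **After exit (a separate matter).** Protocol 13.3 ends follow-up at exit at the latest, apart from the efforts of up to 30 days for early exits. The text below Table 5 in 13.5 ends monitoring at study completion "unless the Investigator determines the event is related to the device, in which case they will be monitored until resolution, if possible". Protocol 11.13.1 says "Upon exiting from the study, no further study data will be collected or study visits will occur for the subject". Together these leave unclear whether the outcome of a device-related event open at exit can be updated later.

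**The case against.** The strongest reply is that the list already contains *Not Recovering/Not Resolved*. Its label fits unchanged chronic pain or a persisting infection, and many investigators would choose it without reading the definition. Nothing gives *Recovering/Resolving* precedence. This stands, and it rules out one tempting inference: that every event ongoing at the end of the study is coded as resolving. The documents show ambiguous coding, not a fixed false coding.

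The second reply concerns consequences. A reader might infer that the study's main safety message would be misstated. The documents do not support that, because no planned summary uses the outcome category. Pain, moreover, is measured by VAS at 12 and 24 months and analysed at each timepoint whatever the AE outcome says. Physical examination, CT and the quality-of-life questionnaire at those visits give further independent information. This reply also stands and limits the effect to one descriptive field.

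The third reply is that 13.3 is more careful than a quick reading suggests, with its exit update and its efforts of up to 30 days for early exits. That is true. However, updating an event at exit does not help if the categories offered for the update are badly defined, and the 30-day provision does not cover subjects who complete month 24.

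Finally, the paper AE form is not among the documents. It may print these definitions, different ones or none, so how sites code in practice cannot be judged from the plan.

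None of these replies answers the basic defect. A label implying improvement has a definition that does not require it, and the neighbouring definition does not clearly take the events that should be kept out.

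**Conclusion.** The concern holds in a limited form. As written, 13.6 permits a persistent, non-improving device- or procedure-related event to be recorded as resolving, and it permits sites to differ on the same state. This is an error in an operational rule, not a missing detail.

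The effect is confined to the AE outcome field and to any listing or narrative that displays it. AE incidence, seriousness, relatedness, the primary endpoint, the sample size and the error rate are untouched. The number of events affected cannot be estimated: the documents give no rate of events persisting to month 24 and no indication of how sites would choose between the two categories.

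The conclusion assumes that sites apply the 13.6 definitions at least some of the time. If the AE form carried clearer definitions, the practical effect would be smaller, but the protocol text would still need correcting.

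The conflict among 11.13.1, 13.3 and 13.5 over events open at exit is real but separate. It is not evidence that outcomes are miscoded.

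**What to change.** Redefine the non-fatal outcomes in Protocol 13.6 by the state of the event at last contact, so that each event fits one category only:

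- *Recovering/Resolving*: improving but not fully resolved.
- *Not Recovering/Not Resolved*: ongoing without improvement, including events left unresolved because no further action is planned (the end state used in 13.3 and 11.13.1).
- Residual effects of an event that is otherwise over: state where they are coded. A separate category is one option, but a sentence assigning them to an existing one would do.

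Bring the paper AE form into line if it reproduces the definitions, and check any events already coded *Recovering/Resolving* against source.

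Separately, reconcile 11.13.1, 13.3 and 13.5 on whether the outcome of a device-related event open at exit is updated afterwards. Which rule should apply is for the sponsor and investigators to decide.

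The cost is a small wording amendment with its usual approval and a review of outcomes already coded. The changes to 13.6 need no new visit, assessment or analysis, and no change to the sample size.

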## **13.7 Study Contact Information**

Questions regarding safety or medical procedures should be directed to Medtronic MITG Medical Affairs. All other questions including emergency contact for reporting serious adverse events and serious adverse device effects should be directed to Medtronic MITG Surgical Innovations, Clinical Research.

## 13.8 Subject Death

All subject deaths must be reported by the investigator to Medtronic on an AE form (AE with outcome of death) as soon as possible after the investigator first learns of the death. In case of death, there should be one AE with the outcome of death.

A copy of the death certificate, if available and allowed by state/local law, should be provided to the Medtronic clinical study team. When a death occurs in a hospital, a copy of the death summary report and all relevant hospital records, if available should be provided to the Medtronic clinical study team. If an autopsy is conducted, a copy of the autopsy report should also be provided to the Medtronic clinical study team if available and allowed by local law. When the death occurs at a remote study site, it is the investigative study site's responsibility to attempt retrieval of information about the death.

In summary, the following data will be collected:

- Date of death
- Detailed description of death
- Cause of death
- Relatedness to system and/or procedure
- Device disposition information
- Death summary/hospital records (if available and allowed by local law)
- Autopsy report (if available and allowed by local law)
- Death certificate (if available and allowed by local law)

## 13.9 Product Complaint Reporting

Product complaint reporting and vigilance reporting are applicable and AEs related to any market-released device during the study must be reported. The reporting of product complaints is not part of the study and should be done in addition to the AE reporting requirements. Refer to local regulations for reporting requirements.

**Product Complaint:** Any written, electronic or oral communication that alleges deficiencies related to the identity, quality, durability, reliability, safety, effectiveness or performance of a medical device that has been placed on the market.

- Abuse: Abnormal use (definition acc. #4.1 of MDR 2.12-1)
- Misuse: Use error (definition acc. #4.20 of MDR 2.12-1)

It is the responsibility of the investigator to report all product complaint(s) associated with a medical device distributed by Medtronic, regardless whether they are related to intended use, misuse or abuse of the product. Reporting must be done immediately and via the regular channels for market-released products. The reporting of product complaints by the clinical team must be done according to the local Standard Operating Procedures. Medtronic will notify the RAs (e.g. CA) as applicable for the following incidents immediately upon learning of them and is not limited to AEs and DDs only:

- Any malfunction or deterioration in the characteristics and/or performance of a device, as well as any inadequacy in the labeling or instructions for use which led or might have led to the death or serious deterioration in the state of health of a patient, user, or other person.
- Any technical or medical reason resulting in withdrawal of a device from the market by the manufacturer.
- Any serious deterioration in the state of health, including:
  - Life-threatening illness or injury
  - Permanent impairment of a body function or permanent damage to a body structure
  - A condition necessitating medical or surgical intervention to prevent permanent impairment of a body function or permanent damage to a body structure

## 14. Data Review Committees

Due to the design of this post-market study in association with Club Hernie, it was determined that a Data Monitoring Committee and Clinical Events Committee would not be chosen specifically, but that the study Steering Committee would review the data as needed. See section 7.3 Study Oversight for details on the Steering Committee.

## 14.1 Safety Committee

An internal Medtronic Safety Team will review the overall rates of protocol defined adverse events (SAEs and events related to the primary and safety endpoints) on a quarterly basis. The committee will have the ability to make recommendations and request further information as required.

# 15. Statistical Design and Methods

## 15.1 General Aspects of Analysis

For each of the objectives the available data will be summarized and missing data will be discussed. The main analysis of the study objectives will be based on available data and missing data will not be imputed unless otherwise noted in the statistical analysis plan. All practical monitoring and follow-up steps will be taken to ensure complete and accurate data collection. Deviations to the statistical analysis plan (SAP) will be reported per section 11.12 (Deviation Handling).

## 15.2 Analysis Execution

Analysis will include both primary and all secondary objectives. A final report will be prepared once all data collection has ended and all subjects have completed the 24-month follow-up or have been exited.

## 15.3 Interim Analysis

After half the enrolled subjects complete the 1-year follow-up timepoint, an interim analysis will be conducted for regulatory purpose. An additional interim analysis for regulatory needs may also be conducted as needed.

## 15.4 Endpoints

### 15.4.1 Primary Endpoints

Statistical analysis of the primary endpoint will be comparative. Binomial one-way test will be used to compare the observed ProGrip™ Self- gripping Polyester Mesh incisional hernia incidence rate to the 20% theoretical incidence rate (from no prevention population), using a two- sided alpha-level of 5%.

### 15.4.2 Other Endpoints

Other endpoints will be analyzed using descriptive methods:

- Qualitative variables will be described by their absolute and relative (%) frequencies of each class or value, and by two-tailed 95% confidence intervals.
- Quantitative variables will be described by their mean, standard deviation (SD), extreme values

(minimum and maximum values), and number of missing data and by two-tailed 95% confidence intervals.

## 15.5 Analysis Sets

- The Performance Analysis Set (PAS) includes all enrolled subjects excluding subjects who became pregnant during the follow-up, or subjects who undergo unscheduled abdominal surgery during study follow-up, which may increase the risk and cause of incisional hernia occurrence\*.

\*Subject follow-up data, starting from the event's occurrence, will be excluded/remove from the performance analysis.

- Per Protocol Analysis Set (PPAS) is a subset of PAS excluding subjects with protocol violation and major protocol deviation(s) that may impact the primary endpoint assessment. More precisely, reason for exclusion may include but is not limited to,
  - Patient wrongly included (*i.e.* patient was enrolled but does not meet all the eligibility criteria).
  - Failure to obtain informed consent.
  - Deviation resulting from device use outside the recommended use in the IFU.
  - Patient who receives the incorrect device or device is misused
- Safety Analysis Set includes all enrolled subjects.

## 15.6 Sample Size Determination

Sample size is determined based on primary performance endpoint, assuming the superiority of ProGrip™ Self-gripping Polyester Mesh use to prevent incisional hernia vs no prevention of incisional hernia within 2-years following a midline laparotomy procedure.

The literature review showed an incisional hernia rate after midline laparotomies around 20% (9-16). Using a power ( $1-\beta$ ) of 80% and a 5% error type I (two-sided), and considering a hypothetical incisional hernia rate of 10% for subjects with ProGrip™ Self-gripping Polyester Mesh, vs a theoretical hypothetical incisional hernia rate of 20% for subjects without any prevention following a midline laparotomy procedure, N= 108 evaluable subjects are required.

Assuming an attrition rate of 20% at 2-years, N=135 subjects will need to be enrolled.

